³ Singleton pregnancies will be identified based on the coding system (e.g., ICD-10) used in the data sources (see [Table 18](#)). All pregnancies will be assumed to be singleton if there is no ICD-10 or procedural code that suggests the pregnancy is multifetal. For RHEKISS singleton pregnancy will be identified with the MedDRA code for single pregnancy. Multifetal pregnancies will be excluded because they share the same maternal exposure and it is not known how medication can be absorbed, distributed, and metabolised by each of the foetuses. Moreover, CMs as well as adverse pregnancy and birth outcomes occur more frequently in twin and triplet pregnancies than in singleton pregnancies, regardless of the exposure to the drug at study.

⁴ IVF pregnancies will be excluded due to issues related to the lack of information regarding maternal covariates in cases where a donor egg was used. Further, a higher incidence of adverse pregnancy and birth outcomes (e.g., gestational diabetes, gestational hypertension, preterm labour, low birthweight) have been reported in IVF pregnancies compared to spontaneously conceived controls ([118](#), [121](#)).

⁵ For example, a patient can be considered continuously enrolled in a specific time period if that patient had a contact with healthcare services (such as drug prescription or hospitalisation) prior to that period and if emigration or death were not notified after this contact. Criteria to define continuous enrolment in the database are country specific and will be detailed in the SAP.

⁶ The exposure period of interest for MCM outcomes is the first trimester of pregnancy and for all other outcomes, anytime during pregnancy. In order to account for potential prescriptions/dispensations/administrations that could lead to an intake during the period of interest, all prescriptions/dispensations/administrations that are recorded in the 16 weeks (time for anifrolumab concentration to fall below the LLOQ for 95% of patients) prior to LMP2 will be considered ([2](#)).

STEP 2B – unexposed to anifrolumab source population

Additional inclusion criteria to be applied after data extraction to create an *unexposed source population* (mirroring the exposed SLE source population, except for the exposure itself):

- Women with a continuous enrolment⁷ in the database for ≥ 12 months prior to LMP2
- Women diagnosed with SLE before pregnancy
- Women treated with SLE SOC during pregnancy⁸

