Additional exclusion criteria to be applied after data extraction to create an *unexposed source population* (mirroring the exposed source population, except for the exposure itself):

- Women treated with anifrolumab during pregnancy and/or during the 16-week period prior to LMP2
- Pregnancies whose date of conception cannot be established

STEP 3

Step to create *exposed to anifrolumab study population* and *unexposed to anifrolumab study population*.

STEP 3A and 3B – exposed and unexposed to anifrolumab study population

Additional inclusion criteria to be applied to the exposed and unexposed source population for creating a post-data extraction overarching *exposed and unexposed study population* with only moderate to severe SLE (mirroring the exposed study population, except for the exposure itself):

- Women with moderate to severe SLE (severity assessment is based on the SLE severity algorithm, see Figure 7)

Additional exclusion criteria to be applied to the exposed and unexposed source population for creating a post-data extraction overarching *exposed and unexposed study population* (mirroring the exposed study population, except for the exposure itself):

- Women with mild SLE (severity assessment is based on the SLE severity algorithm, see Figure 7)

⁷ For example, a patient can be considered continuously enrolled in a specific time period if that patient had a contact with healthcare services (such as drug prescription/administration or hospitalisation) prior to that period and if emigration or death were not notified after this contact. Criteria to define continuous enrolment in the database are country specific and will be detailed in the SAP.

⁸ Exposure to SLE SOC will be assessed from LMP2 until end of first trimester for the outcome of MCM, and from LMP2 until end of pregnancy for all other outcomes. A look-back period of 5-half-lives of relevant drugs will be considered.

- Women with a history of CM or chromosomal abnormalities and genetic syndromes (according to available records)⁹, before delivery
- Women prescribed a confirmed teratogenic drug prior to LMP2 until end of first trimester (for MCM outcome) or end of pregnancy (all other pregnancy outcomes), with a look back period of 5-half-lives of relevant drug, in both the exposed and unexposed groups (see [Table 20](#))

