9.3.1 Exposure definition and measures

Study drugs

Exposure to anifrolumab and other SLE SOC drugs (see [Table 19](#)) will be ascertained from recordings of outpatient visits, procedures, prescriptions, prescriptions dispensed at community pharmacies, or insurance claims registrations, as available in the different data sources.

According to the drug indication, anifrolumab is expected to be prescribed as an IV infusion as part of polytherapy (i.e., add-on therapy to other SLE SOC drugs). However, due to the long study duration, the method of administration may change over time. Therefore, for the main analysis, the objectives will be evaluated in pregnancies exposed to anifrolumab in the polytherapy setting, regardless of administration route.

Despite that anifrolumab is indicated as an add on therapy, it is possible that some patients, either due to incomplete information on medication or off-label use, anifrolumab may be observed to have monotherapy. Therefore, a sensitivity analysis including anifrolumab exposure both as monotherapy and polytherapy will be performed. Details of this sensitivity analysis is provided in [Section 9.7.5](#).

Drug classes used in SLE SOC include antimalarials, glucocorticoids, immunosuppressants (both synthetic and biologic), immunoglobulins and plasmapheresis ([43](#), [55](#), [71](#)) ([Table 19](#)).

Co-medications ([43](#), [55](#)) (prescription drugs other than SLE SOC drugs in [Table 19](#)) are reported in [Table 27](#).

Classification of in utero exposure to SLE drugs and co-medications

The **window of clearance** is defined as 5 times the terminal half-life of the drug for SLE SOC and/or co-medication¹⁰, or, in certain cases, such as biologics, time for concentration to fall below the lowest level of quantification (LLOQ) for 95% of patients. LLOQ is 16 weeks for anifrolumab (2), 14 weeks for belimumab (60) and 15 weeks for rituximab (84).

Particular care will be taken in the definition and classification of *in utero* exposure of the offspring (i.e., through treatment received by the mother during or in the 16 weeks before pregnancy for anifrolumab, 14 weeks for belimumab, 15 weeks for rituximab, and 5-half-lives for other SLE SOC drugs).

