Exposure to SLE SOC and/or co-medication (excluding biologics) will be assessed from LMP2 until end of first trimester for the outcome of MCM, and from LMP2 until end of pregnancy for all other outcomes. A look back period of 5-half-lives of relevant drugs will be considered. This is to account for prescription/dispensations/administrations prior to LMP2 that gave rise to *in utero* exposure of the offspring.

SLE SOC and/or co-medications are assumed to be continued throughout pregnancy. It is common for SLE to be more active during pregnancy with a high prevalence of flares (11, 12, 28, 63, 67). The risk of adverse outcomes among pregnant women who have SLE is related to disease severity (e.g., involvement of the kidneys) and activity during pregnancy (29, 39), thus it is expected that SLE treatment would occur even in pregnancy. A sensitivity analysis accounting for actual use of SLE SOC during pregnancy is presented in Section 9.7.5.

Exposure to anifrolumab will be assessed from LMP2 until end of the first trimester for the outcome of MCM, and from LMP2 until end of pregnancy for all other outcomes (see Section 8.1), or until censoring, regardless of duration of exposure. Considering anifrolumab window of clearance (16 weeks, see definition above), all patients who receive prescriptions/dispensations/administrations of anifrolumab in the 16 weeks prior to LMP2 or during pregnancy will be considered exposed (2).

Offspring whose mother had no anifrolumab prescription/dispensations/administration in the 16 weeks prior to LMP2 or during the first trimester for the outcome of MCM, or during pregnancy for all other outcomes, will be considered unexposed.

Although, the foetus is most at risk during the period of organogenesis (i.e., during the first trimester of pregnancy), exposures during other gestational time periods may also be associated with adverse outcomes (e.g., spontaneous abortion, stillbirth, or other pregnancy complications). The identification of critical windows of exposure *in utero* provides clues to possible mechanisms of the pregnancy loss and provides guidelines for protection of the foetus. An exploratory analysis focusing on the effect of *in utero* exposure to anifrolumab in different trimesters of pregnancy on the

¹⁰ The respective half-lives of SLE SOC and co-medications will be provided in the SAP.

occurrence of select pregnancy loss outcomes (composite of spontaneous abortion and stillbirth will be assessed:

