- **Exposed during pregnancy by trimesters** – *in utero* exposed to anifrolumab will be determined for each pregnancy trimester (dichotomous variables) and combined into a pattern of exposure by trimester (Table 6). The exposure by trimester will be defined as:
 - in each trimester, offspring whose mother had at least one prescription/dispensations/administration of anifrolumab leading to an exposure period overlapping with a specific trimester(s), will be classified as exposed (yes/no) (Table 6);
 - offspring whose mother had no anifrolumab prescription/dispensations/administration in the 16 weeks (anifrolumab window of clearance) prior to LMP2 or during all pregnancy, with the assumption of continuing treatment with SOC, will be classified as non-exposed (yes/no) (Table 6).

Table 6: Maternal exposure status by trimester, offspring *in utero* exposed to anifrolumab (polytherapy) vs offspring *in utero* exposed to SLE SOC

Exposed group				Comparator group		
1 st trimester	2 nd trimester	3 rd trimester		1 st trimester	2 nd trimester	3 rd trimester
anifrolumab (+ SOC)	SOC ¹	SOC ¹	VS	SOC	SOC ¹	SOC ¹
anifrolumab (+ SOC)	anifrolumab (+ SOC)	SOC ¹	VS	SOC	SOC	SOC ¹
anifrolumab (+ SOC)	anifrolumab (+ SOC)	anifrolumab (+ SOC)	VS	SOC	SOC	SOC
SOC	anifrolumab (+ SOC)	anifrolumab (+ SOC)	VS	SOC	SOC	SOC
SOC	SOC	anifrolumab (+ SOC)	VS	SOC	SOC	SOC

Abbreviations used in the table: SOC, Standard of care; VS, Versus

¹ SOC might not be applicable if pregnancy ends early

Definition of exposure period

Women exposed to anifrolumab during pregnancy are included in the exposed groups regardless of the exposure status before pregnancy. The maximum exposure period is from LMP2 to delivery/birth. The maternal exposure period during pregnancy is not considered to be fixed. This is because pregnancy duration is not exactly the same for all pregnancies (full-term birth is considered between 37 to 42 weeks of gestation). Also, exposure period can end earlier with a censoring event (e.g., elective termination of pregnancy).

The definition of exposure period relies on available information on the date of prescription/dispensation/administration, the expected supply (i.e., package size, the number of packages prescribed/dispensed), and the estimated window of drug clearance (for anifrolumab, the time for concentration to fall below the LLOQ for 95% of patients is 16 weeks from last administration). The exposure period starts on the date when the drug was administered or

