prescribed/dispensed (if information on the date of dispensation is not available, the start of the exposure period will be defined based on the date when the prescription was issued). The end date of the exposure period is calculated by adding the estimated window of clearance and expected supply to the prescriptions/dispensations/administrations date (Figure 6).

[figure not shown]

Figure 6: Anifrolumab exposure period

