9.7.5 Sensitivity analyses

Re-definition of the pre-conception exposure window for patients who receive prescriptions/dispensations/administrations of anifrolumab in the period prior to LMP2

The rationale for this sensitivity analysis is to explore the robustness of the exposure definition to changes in the pre-conception exposure ascertainment time-window for patients who receive anifrolumab prior to LMP2. While it is reasonable to assume that an unborn child could be exposed to anifrolumab if the mother has had a dose of anifrolumab in the 16 weeks prior to conception (LMP2), based on the population pharmacokinetics of anifrolumab, where time for concentration to fall below the LLOQ for 95% of patients is 16 weeks (2), it is also plausible that the serum concentrations may be so low (or even absent) at the time of pregnancy. Therefore, using the exposure ascertainment period of 16 weeks prior to LMP2 could result in exposure misclassification. There is a possibility that this misclassification could affect the measure of association between the exposure of interest and the outcomes of interest.

Therefore, to reduce the potential risk of exposure misclassification, the following alternative pre-conception time-windows for anifrolumab exposure will be considered:

- a) up to 8 weeks prior to LMP2 until end of the first trimester for the outcome of MCM, and up to 8 weeks prior to LMP2 until end of pregnancy for select pregnancy loss outcomes (composite of spontaneous abortion and stillbirth).
- b) from LMP2 until end of the first trimester for the outcome of MCM, and from LMP2 until end of pregnancy for select pregnancy loss outcomes (composite of spontaneous abortion and stillbirth).

Re-definition of the pre- and post-conception exposure window for the exclusion of SLE SOC and non-SLE SOC drugs with a confirmed teratogenic effect

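### Section 9.3.1 gives two anifrolumab exposure rules, one by record date and one adding supply to clearance; they disagree for any record that carries supply

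*Protocol*

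**What the plan says.** Two ways of fixing exposure status stand side by side in the protocol.

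**By record date.** Section 9.3.1 (classification of in utero exposure) says that patients with "prescriptions/dispensations/administrations of anifrolumab in the 16 weeks prior to LMP2 or during pregnancy will be considered exposed". The unexposed are the mirror image: "Offspring whose mother had no anifrolumab prescription/dispensations/administration in the 16 weeks prior to LMP2" or during the first trimester (MCM) or pregnancy (other outcomes). The abstract repeats this. Footnote 6 in section 9.2.2 shows that the window applies to the record, since it counts "all prescriptions/dispensations/administrations that are recorded in the 16 weeks" before LMP2. Supply plays no part.

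**By exposure period.** Under the heading on the definition of the exposure period, section 9.3.1 says: "The end date of the exposure period is calculated by adding the estimated window of clearance and expected supply to the prescriptions/dispensations/administrations date". The inputs include "the expected supply (i.e., package size, the number of packages prescribed/dispensed"), and the 16 weeks of clearance are counted from the last administration.

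A third wording speaks of treatment. STEP 2B in section 9.2.2 excludes from the comparators "Women treated with anifrolumab during pregnancy and/or during the 16-week period prior to LMP2", and section 9.3.1 elsewhere refers to treatment received in the 16 weeks before pregnancy.

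The main analysis takes any route of administration, because "due to the long study duration, the method of administration may change over time". Section 9.7.5 plans two narrower windows, 8 weeks before LMP2 and, as variant (b), "from LMP2 until end of the first trimester for the outcome of MCM" (to end of pregnancy for pregnancy loss). Neither mentions supply.

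**The concern.** For a single infusion the first two rules coincide. For a dispensed or prescribed multi-dose supply they do not: the record can be older than 16 weeks while the exposure period, as the protocol computes it, still reaches past LMP2. Read by record date, such a pregnancy leaves the exposed group and can enter the comparator group of both primary analyses.

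Mixing exposed pregnancies into the comparators pulls the RR towards 1. Because the study is sized to rule out an RR of 2.5, that error favours a reassuring conclusion. The woman can plausibly reach the comparator group: an anifrolumab prescription is one of the criteria in the adapted severity algorithm, which looks back 12 months (section 9.3.3), so the same record that is too old to make her exposed can help qualify her as moderate to severe. She would also need SLE SOC.

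**Working it through.** No sample size or power figure in the protocol depends on this point. The check is date arithmetic, followed by a bound on the dilution.

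**Inputs.** Clearance of 16 weeks and the two rules (section 9.3.1); 10% of pregnancies exposed (section 9.5.1.1); RR threshold of 2.5 (section 9.5). The protocol gives no supply length, so S = 0, 4, 8 and 12 weeks are assumed.

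**Where the rules disagree.** Let d be the weeks from record to LMP2.
- Record rule: exposed if d ≤ 16.
- Exposure period: ends at −d + S + 16 weeks relative to LMP2, so it passes LMP2 if d < 16 + S.
- Disagreement: 16 < d < 16 + S.

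| S (weeks) | Records in dispute (weeks before LMP2) |
|---|---|
| 0 | none |
| 4 | more than 16, less than 20 |
| 8 | more than 16, less than 24 |
| 12 | more than 16, less than 28 |

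Example: d = 18, S = 4. The period ends at −18 + 4 + 16 = 2 weeks after LMP2, yet no record falls in the 16-week window.

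**Trimester analysis.** Section 9.3.1 defines the exposed group by overlap of the exposure period with a trimester, and the non-exposed group by absence of a record in the 16 weeks before LMP2 or during pregnancy. The example overlaps the first trimester and has no such record, so it satisfies both definitions.

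**Variant (b) in section 9.7.5, if read by record date.** A woman dispensed 12 weeks of product 6 weeks before LMP2 has supply until −6 + 12 = 6 weeks after LMP2. With no later record she would not count as exposed in variant (b), although her supply runs past conception. Read by exposure period, she is exposed.

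**Bound on the dilution.** Assume that all use is dispensed, that 10% of pregnancies are exposed, that all exposure comes only from pre-LMP2 records spread evenly over the 16 + S weeks, and that misplaced women carry the full exposed risk.
- Misplaced share of the exposed: S/(16+S).
- Share of comparators truly exposed: f = 0.10 × S/(16+S) ÷ [0.90 + 0.10 × S/(16+S)].
- Apparent RR when the true RR is 2.5: 2.5/(1 + 1.5f).

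| S | S/(16+S) | f | Apparent RR |
|---|---|---|---|
| 4 | 0.200 | 0.020/0.920 = 2.2% | 2.5/1.0326 = 2.42 |
| 8 | 0.333 | 0.0333/0.9333 = 3.6% | 2.5/1.0536 = 2.37 |
| 12 | 0.429 | 0.0429/0.9429 = 4.5% | 2.5/1.0682 = 2.34 |

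Propensity-score matching is ignored.

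**The case against.** The strongest reply is that this concerns a formulation not yet in use. The only current route named is IV infusion, and the planned capture is largely by administration: Danish hospital medication data, Finnish electronic records, the French high-cost list and US procedure codes. With supply zero the rules agree. This stands, and it limits the practical weight. It does not remove the conflict, because the protocol admits any route, lists prescriptions and pharmacy dispensing as exposure sources, and writes supply into the exposure period.

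A reader might infer that women in the disputed band are still dosing at conception. The documents do not support that for the main analysis. Supply there ends at d − S weeks before LMP2: 12 to 16 weeks before for S = 4, and 4 to 16 weeks before for S = 12. These women are in the clearance tail, and section 9.7.5 itself accepts that concentrations may then be very low or absent. Use continuing past LMP2 arises only in variant (b), and only if that window is read by record date, which section 9.7.5 does not say.

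It can also be said that the STEP 2B wording tests treatment, so a woman whose supply reaches into the 16 weeks would be excluded from the comparators. That is a fair reading and would match the exposure-period rule. But it contradicts footnote 6 and the unexposed rule in section 9.3.1, so it adds a third wording without settling the matter.

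Finally, Figure 6 is not visible in the text reviewed, and section 9.7 leaves data derivations to the SAP. Either might illustrate the calculation, but the protocol text already fixes both rules, and nothing visible says which one governs.

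**Conclusion.** The inconsistency is real and should be corrected. It affects any record with supply dated more than 16 but less than 16 + S weeks before LMP2, and it leaves the trimester groups not mutually exclusive. The effect is nil for infusions dated at administration.

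For dispensed product the bias is towards RR 1, of unknown and probably small size. The bound of 2.2% to 4.5% contaminated comparators (apparent RR 2.42 to 2.34) rests on assumptions chosen to be extreme. A reader might take the shares S/(16+S), 20% to 43%, as the expected loss of exposed pregnancies. They are not: they apply only to women exposed solely through a pre-LMP2 dispensing and need evenly spread record dates. Section 9.5.1.1 instead expects mostly unplanned pregnancies exposed in the early stages, which suggests records near or after LMP2. Nor can it be said outright that the 9.7.5 analyses worsen misclassification; that holds only under the record-date reading. The stated power figures are unaffected, since they assume a true RR of 1.

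**What to change.** Use one rule in sections 4, 9.2.2 (including footnote 6, STEP 2A and 2B, and Table 5), 9.3.1 and 9.7.5:

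- A pregnancy is exposed if an exposure period (record date + expected supply + 16 weeks) overlaps the relevant window: LMP2 to end of first trimester for MCM; LMP2 to end of pregnancy or outcome otherwise. State that a period ending exactly at LMP2 counts, so that the rule reduces to the present 16-week look-back when supply is zero.
- A pregnancy is unexposed only if no such period overlaps. Apply the same test to the non-exposed group in the trimester analysis.
- In section 9.7.5, count the 8-week and LMP2 windows from the end of supply (the estimated last administration), not from the record date.

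The cost is wording in the protocol, carried into the SAP. The supply fields are already named as inputs in section 9.3.1, and no sample size changes. It should be settled before data extraction, because the look-back for dispensed product becomes 16 + S weeks (20, 24 or 28 weeks for the supplies assumed here).

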9.3.2 Outcome definition and measures

In line with the study objectives (see Section 8.1), the study’s primary, secondary and exploratory outcomes are defined below. Study outcomes will be identified based on the coding system used in the data sources (ICD-10 CM for the USA data sources, ICD-10 for Denmark, Finland and France; MedDRA codes for Germany). ICD-10 codes are provided in [Appendix D. Exemplar Codelists](#).

The maternal death rate in women with SLE as well as the infant death rate of women with SLE are reported to be low and thus, the maternal and infant death rates are expected to be low in this study (21, 99).

Primary outcomes

During the outcome ascertainment period, which will span from the index date to the exit date for each offspring, outcome events will be identified in registers and data sources using ICD-10 or equivalent codes (ICD-10 CM for the USA data sources, ICD-10 for Denmark, Finland, and France; MedDRA codes for Germany). For the primary outcome the **index date/start of follow-up**, included in the enrolment, will be defined as the LMP2 (as defined in Section 9.1) from which the foetus/offspring will be followed up for the outcome of interest. The **exit date/end of follow-up** will be defined as the first of the following: end of the study period, death, emigration (where available), loss to follow-up (disenrollment/de-registering), reaching the age of 1 year or date of first diagnosis of the outcome at study.

MCM (defined as a composite of all major MCMs) among live and non-live offspring: The first primary outcome of interest is MCM occurring in live or non-live offspring. MCM is defined as defects of prenatal origin that have either cosmetic or functional significance to the child's health, development, or survival. MCM ascertainment will be based on the presence of an ICD-10 code (or other database specific coding system [codes to be adapted to the coding systems used in each of the data sources]) in the database. These ICD-10 codes will be classified according to the EUROCAT (Description of the Congenital Anomaly Subgroups in EUROCAT Guide 1.5) classification scheme, as four of the five data sources are in Europe (41). As there are some differences in the classification of MCMs by different classification schemes, the USA CDC definition of MCM as an abnormality of body structure or function that is present at birth, is of prenatal origin (i.e., birth defect), has significant medical, social, or cosmetic consequences for the affected individual, and typically requires medical intervention as implemented by the Metropolitan Atlanta Congenital Defects Program (MACDP) will also be implemented as a sensitivity analysis (see Section 9.7.5) (15, 24). The list of the MCM and their respective ICD-10 codes are presented in Table 22a using the EUROCAT classification. The MACDP 6-digit code defect list for major congenital malformations is presented in Table 22b.

The MCM ascertainment period is defined as:

- for live births, from birth until 1 year of age
- for non-live births (spontaneous abortion and stillbirth) an ICD-10 of MCM as the diagnosis at end of pregnancy
- for elective terminations, an ICD-10 code of an MCM as the reason for the termination at termination of pregnancy.

Select pregnancy loss outcomes (composite of spontaneous abortion and stillbirth) among all pregnancies

The second primary outcome of interest is select pregnancy loss outcomes, a composite of spontaneous abortion and stillbirth (Table 24).

For the select pregnancy loss outcomes, the **index date/start of follow-up**, will be defined as the LMP2 (as defined in Section 9.1) from which the pregnancy will be followed until the outcome of interest. The **exit date/end of follow-up**¹¹ will be defined as the end of the study period, death, emigration (where available), loss to follow-up (disenrollment/de-registering), or date of first diagnosis of the outcome at study, or delivery, whichever is the earliest.

The select pregnancy loss outcomes will be defined as the presence of at least one of the following criteria:

- ICD-10 code of spontaneous abortion¹² (unintended loss of an intrauterine pregnancy) which is less than 22 weeks of gestation for the European data sources (40); less than 20 weeks for the USA data sources (64);
- ICD-10 code of stillbirth¹³ (unintended foetal death occurring at or after 22 weeks of gestation for the European data sources (78); at or after 20 weeks for the USA data sources (64).

Secondary outcomes

During the outcome ascertainment period, outcome events will be identified based on ICD-10 CM codes for the USA, ICD-10 for Denmark, Finland and France; MedDRA codes for Germany recorded in patient registries.

Minor congenital malformations

For this outcome the **index date/start of follow-up**, will be defined as the LMP2 (as defined in Section 9.1) from which the foetus/offspring will be followed up for the outcome of interest. The **exit date/end of follow-up** will be defined as the end of the study period, death, emigration (where available), loss to follow-up (disenrollment/de-registering), reaching the age of 1 year or date of first diagnosis of the outcome at study, whichever is the soonest.

¹¹ Specific outcome censoring rules will be applied. For spontaneous abortion outcome specific end of follow-up will be 22 weeks of gestation for the European data sources or 20 weeks for the USA data sources further details will be specified in the SAP.

¹² The legal requirements and conventional definitions for spontaneous abortion vary by country. The definition used by the data source will be applied. The National Center for Health Statistics (NCHS) and the Center for Disease Control and Prevention (CDC) define spontaneous abortion in the USA as a pregnancy termination before 20 weeks of gestation or a foetus weighing 500 grams at birth. The ICD-10 defines spontaneous abortion as "the loss of pregnancy from natural causes before the 20th week of pregnancy". The WHO defines spontaneous abortion as "termination of pregnancy by expulsion of the embryo or foetus before 22 weeks of pregnancy or below 500 g of weight." The EurPeristat defines spontaneous abortion as the termination of a pregnancy before 22 weeks of gestation.

¹³ The legal requirements and conventional definitions for stillbirth vary by country. The definition used by the data source will be applied. Stillbirth is defined as foetal death whose birth weight is of 350 g or more, or if weight is unknown, of 20 completed weeks gestation or more, by the CDC. Stillbirth is defined by the WHO and ICD-10 as the death of a foetus before complete expulsion or extraction from its mother after reaching a birth weight of 500 grams or gestational age of 22 weeks. The EurPeristat defines stillbirth as the death after 22 completed weeks of gestation.

mCM among live and non-live offspring: are a structural anomaly or dysmorphic observable feature which does not impair viability or require intervention or treatment. mCM will be defined as a composite, classified according to EUROCAT (Description of the Congenital Anomaly Subgroups in EUROCAT Guide 1.5) (41). The list of the mCM and their respective ICD-10 codes are presented in [Table 23](#).

Adverse pregnancy outcomes

For the adverse pregnancy outcomes, the **index date/start of follow-up**, included in the enrolment, will be defined as the LMP2 (as defined in section 9.1) from which the pregnancy will be followed up for the outcome of interest. The **exit date/end of follow-up**¹⁴ will be defined as the end of the study period, death, emigration (where available), loss to follow-up (disenrollment/de-registering), or date of first diagnosis of the outcome at study, or delivery, whichever is the earliest. The list of the adverse pregnancy outcomes¹⁵ and their respective ICD-10 codes are presented in [Table 24](#).

- **Spontaneous abortions**¹²: unintended loss of an intrauterine pregnancy which is less than 22 weeks of gestation for the European data sources (40); less than 20 weeks for the USA data sources (64);
- **Ectopic pregnancy:** occurs when a fertilised egg implants outside of the uterus, usually in one of the fallopian tubes.
- **Elective termination of pregnancy:** is defined as the intentional termination of pregnancy at any time in gestation for any reason. When possible, reasons for elective termination are captured and classified as elective termination of pregnancy for foetal anomaly or for other reasons.
- **Stillbirth**¹³: unintended foetal death occurring at or after 22 weeks of gestation for the European data sources (78); at or after 20 weeks for the USA data sources (64).
- **Composite of foetal loss:** will be defined as the presence of at least one of the following: spontaneous abortion, ectopic pregnancy, elective termination of pregnancy and stillbirth.
- **Infections requiring hospitalisation during pregnancy:** infections requiring hospitalisation during pregnancy will be considered as the occurrence of the first event of a hospitalisation for an infection diagnosis, as primary diagnosis. The list of the infections considered, and their respective ICD-10 codes are presented in [Table 24](#).
- **Emergency caesarean section:** surgical procedure involving the incision of the walls of the abdomen and uterus for delivery of an offspring that occurs when vaginal delivery is

¹⁴ Specific outcome censoring rules will be applied. For spontaneous abortion and ectopic pregnancy there will be outcome specific end of follow-up dates. For spontaneous abortion outcome specific end of follow-up will be 22 weeks of gestation as for the ectopic pregnancy end of follow-up will be 16 weeks of gestation further details will be specified in the SAP.

¹⁵ To maximize the capture of non-live births for spontaneous abortion, elective termination, and stillbirth, an exhaustive list of codes related to pregnancies as well as to outcomes will be used, i.e., every code will be included.

discontinued due to unexcepted complications during labour, such as the occurrence of foetal distress (105).

Adverse birth outcomes

For the adverse birth outcomes, the **index date**, included in the enrolment, will be defined as the delivery/birth date from which the offspring will be followed up for the outcome of interest. The **exit date/end of follow-up** will be defined as the end of the study period, death, emigration (where available), loss to follow-up (disenrollment/de-registering), or 1 day after delivery/birth, whichever is the soonest. The list of the adverse birth outcomes and their respective ICD-10 codes are presented in [Table 25](#).

- **Preterm birth:** defined as live births less than 37 weeks of gestation (<37 weeks)
- **SGA:** is defined as a birth weight lower than the 10th percentile of the distribution of birth weights among live births, by gestational age and sex, using a validated global reference for foetal weight and birthweight (76).

Exploratory outcomes

For the exploratory outcomes, the **index date/start of follow-up** and **exit date/end of follow-up** for MCM will be defined as in Section 9.3.2 MCM will be classified also by body system organ class according to the EUROCAT categories Guide 1.5 (section 3.3 in EUROCAT Subgroups of congenital anomalies) (41).

The full list of ICD-10 codes for MCM of interest can be found in Table 22.

Adverse outcomes related to infant growth up to 1 year of age

For the adverse outcomes related to infant growth, the **index date/start of follow-up**, included in the enrolment, will be defined as birth date from which the offspring will be followed up for the outcome of interest. The **exit date/end of follow-up** will be defined as the end of the study period, death, emigration (where available), loss to follow-up (disenrollment/de-registering), reaching the age of 1 year or date of first diagnosis of the outcome at study, whichever is the soonest.

Infant growth up to one year of age:

- Length (any time point during the first year of life – as available)
- Weight (any time point during the first year of life – as available)
- Head circumference (any time point during the first year of life – as available)

Adverse outcome related to growth up to one year of age will be a dichotomous variable defined as a composite outcome based on the presence of at least one of the following conditions: abnormal head circumference growth, stunting, or wasting. The period of assessment will be during the first year of life and the outcome will be assessed whenever anthropometric measurements are

available. The offspring will be classified as subnormal growth if meeting at least one of the recommended WHO cut off values below at any time during the first year of life (119):

- <-2 SD z-score (equivalent to 2.3rd percentile) of head circumference-for-age based in the WHO 2006 growth charts.
- <-2 SD z-score (equivalent to 2.3rd percentile) of length-for-age to define stunting based in the WHO 2006 growth charts.
- <-2 SD z-score (equivalent to 2.3rd percentile) of weight-for-length to define wasting, based in the WHO 2006 growth charts (119).

